5.4.2 Secondary effectiveness measures

Secondary effectiveness assessments were based on the full analysis set (FAS) and the permissible set (PPS).

- Objective response rate (ORR)
- Tumor disease control rate (DCR) at 1 month during follow-up period
- Tumor markers (if required)
- Ease of use (ProBeam360 System, radiotherapy management software (Aria), Treatment Planning System (Eclipse))

The 95% confidence interval was calculated by Clopper-Pearson for the above secondary efficacy indicators of "objective response rate (ORR)" and "tumor disease control rate (DCR) during the follow-up period of 1 month".

For the "time to sustained response (DOR)" secondary efficacy measure, describe the sustained response.

Descriptive statistics were performed on the percentage of measurable tumor longest diameter sum (SLD) from baseline, and a waterfall chart was made for the maximum percentage reduction of SLD in each subject compared with the screening period.

For the secondary efficacy indicators of "tumor markers" and "tumor-specific symptoms", the changes before and after are described, and the changes are described in the table.

For the secondary efficacy index of "product ease of use", the scores of each category and the total score were calculated, and the details of the open questions were described in a table.

5.5 Safety evaluation index

The safety metrics are based on the Safety Dataset (SS).

The main safety indicators included the proportion of CTCAE grade 3 toxicity and the proportion of CTCAE grade 4 and 5 toxicity.

Secondary safety measures included the proportion of CTCAE grade 1 and 2 toxicity, laboratory tests, ECOG performance status classification, tumor recurrence rate, adverse events, serious adverse events, and device defects.

5.5.1 Proportion of CTCAE toxicity

The severity of AEs was assessed according to Common Adverse Event Common Terminology Criteria (CTCAE) V5.0.

Grade 1: mild, asymptomatic or mildly symptomatic, clinical or diagnostic findings only, no treatment required;

Level 2: moderate, minimal, localized, or non-invasive interventions, age-related limitations in instrumental activities of daily living (ADLs) (instrumental ADLs refer to cooking, grocery or clothing shopping, phone access, financial management, etc.);

Grade 3: severe or medically significant, but not immediately life-threatening, hospitalization or prolonged hospital stay, disability, restriction of self-care ADL (self-care ADL refers to bathing, dressing and undressing, eating, toileting, taking medications, not being bedridden);

Grade 4: life-threatening; requiring urgent intervention;

Grade 5: AE-related death.

The number and percentage of subjects who achieved each grade of CTCAE toxicity were calculated, and the details of toxicity were described in a table.

5.5.2 Laboratory tests

The results of laboratory indicators (blood routine, coagulation routine, urine routine, blood biochemistry) and their changes from baseline were summarized and described at each planned visit, the changes before and after treatment were evaluated, and the pre- and post-treatment cross-over tables of clinical evaluation (normal, abnormal and clinically significant) were given.

5.5.3 ECOG Grade of Strength Status

Summarize and describe the ECOG physical status classification for each program visit.

5.5.4 Adverse events

The incidence, occurrence and severity of adverse events and serious adverse events were summarized by

descriptive statistics and MedDRA (V25.0) medical terminology according to system organ classification.

- (1) The number (incidence) and number of AEs of various types of AEs are summarized and described, including all AEs, TEAEs, TEAEs related to investigational medical devices, SAEs, and SAEs related to investigational medical devices.

Treatment Emergent Adverse Event (TEAEs) are defined as unfavorable medical events occurring between the start of proton therapy in clinical study subjects and the end of the trial, regardless of whether they are treatment related.

Definition of Treatment-Period Adverse Events Related to Investigational Medical Devices:
Treatment-period adverse events that are "definitely related", "probably related", "probably related" to the investigational medical device.

- (2) For the types of AEs described in (1), the number of occurrences (incidence) and the number of cases of each classification are described based on the classification of system organ classification (SOC) and preferred term (PT).
- (3) For the types of AEs described in (1), the number of occurrences (incidence) and cases of different severity of each classification are described based on the classification and severity of the system organ classification (SOC) and preferred term (PT).
- (4) A list of AEs, TEAEs, TEAEs related to investigational medical devices, SAEs, and SAEs related to investigational medical devices is listed, including but not limited to the name of adverse events, severity, relationship to trial operation, AE start date and end date, etc.

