2.1 Objective

Clinical trial (screening-short-term follow-up): The data obtained by using Proton Beam equipment (ProBeam360) for radiation therapy in tumor patients compared with the target value to evaluate the effectiveness and safety of ProBeam360 for radiation therapy in tumor patients to provide clinical basis for product registration application.

Long-term follow-up: The long-term efficacy and safety of ProBeam360 for radiation therapy in cancer patients were evaluated by using the long-term follow-up data of ProBeam360 for radiation therapy in cancer patients.

2.2 content

This clinical trial is a prospective study, carried out in 1 clinical trial institutions, and 47 patients with tumors of intracranial, head and neck, chest, abdomen, spine, pelvis, limbs and other tumors were selected as study subjects, all using investigational medical devices, and designed for a single group of target values. The research device involved in this trial is the proton therapy device (ProBeam360), a medical device for investigation. Short-term follow-up is: 1 visit during the screening period (within 4 weeks before the first treatment), 2~9 visits during the treatment period according to the length of treatment weeks (1~8 weeks), and 3 after the last treatment 3 visits within a month; Long-term follow-up was 11 visits over a period of 3~5 months after the end of the last treatment. The main efficacy evaluation index was DCR 3 months after the end of the last treatment, and the main safety evaluation index was the proportion of CTCAE grade 3 toxicity in the entire short-term follow-up clinical trial cycle and CTCAE grade 4 & 5 toxicity reactions in the entire short-term follow-up clinical trial cycle. The collected data were analyzed and compared with the target values, and the effectiveness and safety of ProBeam360 in proton radiation therapy for patients with tumors such as intracranial, head and neck, chest, abdomen, spine, pelvis, and extremities were evaluated.

3 Overall design

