3.1.5 Safety evaluation methods

If it is not possible to follow up at the clinical trial center according to the visit arrangement due to the epidemic, the clinical examination can be examined by other tertiary hospitals, and the test results will be transmitted back to the clinical trial center for evaluation; The carrier of imaging data in the outer hospital is not limited, and it is necessary to ensure that the imaging department of the center can be opened and read.

3.1.5.1 The main safety evaluation indicators and the methods and time selection of their evaluation, recording and analysis

(1) CTCAE 3 toxicity ratio

Reason for selection: According to the Guidelines for the Technical Review of Clinical Evaluation of Proton Carbon Ion Therapy System (CFDA Circular No. 4 of 2018), if the proportion of CTCAE grade 3 acute toxic reactions exceeds 5%, it is considered as a clinical trial failure, so it is selected. The proportion of CTCAE grade 3 toxicity is used as the main safety evaluation index, and CTCAE is a commonly used safety evaluation standard in radiation oncology, which is widely recognized and applied by clinicians.

Indicator definition: Proportion of subjects with grade 3 toxicity during the trial cycle.

Metric type: Qualitative.

Data collection time: the entire clinical trial cycle.

Evaluation time: 3 months \pm 7 days after the last treatment.

Evaluation methodology: Investigators recorded AEs that occurred during the clinical trial cycle and graded them according to CTCAE V5.0.

Calculation formula: proportion of CTCAE grade 3 toxicities = (number of subjects with CTCAE grade 3 toxicity in the test cycle) / total number of subjects \times 100%.

Judging criteria: See CTCAE V5.0 for details.

(2) CTCAE Grade 4 and 5 toxicity ratio

Reason for selection: According to the Guidelines for the Review of Clinical Evaluation Technologies of Proton Carbon Ion Therapy System (CFDA Circular No. 4 of 2018), CTCAE grade 4 and 5 toxicities are considered to be clinical trial failures, so 4 is selected. The proportion of grade 4 and grade 5 toxicity reactions is used as a safety evaluation index, and CTCAE is a commonly used safety evaluation standard in radiation oncology, which is widely recognized and applied by clinicians.

Indicator definition: Proportion of subjects with toxicity of grade 4 and 5 during the trial cycle.

Metric type: Qualitative.

Data collection time: the entire clinical trial cycle.

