DCR	Disease Control Rate	Tumor disease control rate
ECOG	Eastern Cooperative Oncology Group	Eastern Oncology Collaborative Group
FAS	Full Analysis Set	Full analysis set
ICH	The International Council for Harmonisation of Technical Requirement for Pharmaceuticals for Human Use	International Harmonization Council for Technical Requirements for Pharmaceuticals for Human Use
MedDRA	Medical Dictionary for Regulatory Activities	Medical Dictionary of Regulatory Activities
NYHA	New York Heart Association	New York Heart Society
ORR	Objective Response Rate	Objective response rate
PD	Progressive Disease	Disease progression
PET	Positron Emission Tomography	Positron emission tomography
PN	Preferred Name	Preferred name
PPS	Per-Protocol Set	Conforms to the scenario set
PR	Partial Response	Partial relief
PSA	Prostate Specific Antigen	Prostate-specific antigens
PT	Preferred Terms	Preferred term
SAE	Serious Adverse Events	Serious adverse events
SAP	Statistical Analysis Plan	Statistical analysis plan
SAS	Statistical Analysis System	Statistical analysis system
SD	Stable Disease	Stable disease
SLD	Sum of Longest Diameter	Sum of longest diameters of tumors
SOC	System Organ Class	Systematic organ classification
SS	Safety Set	Security datasets
TEAE	Treatment Emergent Adverse Event	Adverse events during the treatment period
TNM	Tumor, Node, Metastasis	Tumors, lymph nodes, metastases
WHODD	World Health Organization Drug Dictionary	World Health Organization Dictionary of Medicines
WOCF	Worst Observation Carried Forward	Worst observed data carryover

This statistical analysis plan (SAP) refers to the E9 guiding principles of the International Council for Harmonization of Technical Requirements for Pharmaceuticals for Human Use (ICH) Guidance for Industry: Statistical Principles for Clinical Trials ICH E3 Guidance for Industry: Structure and Content of Clinical Study Reports Relevant national regulations and guidelines, according to the clinical study protocol titled "Varian ProBeam360 Proton Therapy System China Clinical Trial (Wuhan)" (version number: V1.0, Version Date: 2024-01-12) developed.

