4.2 Handling of missing dates for various events

For various events (previous/concomitant medications, concomitant treatments, AEs, etc.), according to the definition and nature of different events, the fill-in rules for the absence of their start/end dates are agreed. If the end date of each event is missing, it will not be filled, and the rules for missing the start date are shown in Table 2.

Table 2 Incomplete filling rules with start dates

Missing values	Fill the rules
day	If the year and month are the same as the year and month of the treatment start date, and the end date is after the treatment start date or is missing, the treatment start date is used to fill in; Otherwise fill for 1 day.
Day/Month	If the year is the same as the treatment start date, and the end date is after the treatment start date or is missing, the treatment start date is used to fill in; Otherwise fill for January 1.
Day/Month/Year	If the end date is after the treatment start date or is missing, the treatment start date is used to fill in; Otherwise, no filling will be carried out.

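### The SAP's TEAE definition has no worsening clause, so an AE that begins in screening and rises in grade under proton therapy can be left out of the TEAE and device-related TEAE tables

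*SAP*

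**What the plan says.** SAP 5.5.4 defines TEAEs by a time window alone: "unfavorable medical events occurring between the start of proton therapy in clinical study subjects and the end of the trial", whatever their relation to treatment. The gloss in the SAP abbreviation list is just as silent on worsening: "Adverse events during the treatment period". The paragraph headed "Definition of Treatment-Period Adverse Events Related to Investigational Medical Devices" keeps the treatment-period events with a qualifying causality rating, so it inherits the same window. The categories to be summarised, overall and by SOC, PT and severity, are given as "including all AEs, TEAEs, TEAEs related to investigational medical devices, SAEs, and SAEs related to investigational medical devices".

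SAP 4.2 sets the date rules for AEs and acts only on incomplete start dates. If just the day is missing, the month and year match treatment start, and the event had not ended before treatment, "the treatment start date is used to fill in; Otherwise fill for 1 day". A complete start date is left as recorded.

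On collection, Protocol 3.1.5.1 states: "Investigators recorded AEs that occurred during the clinical trial cycle and graded them according to CTCAE V5.0". Protocol 2.1 takes the clinical trial to run from screening to short-term follow-up.

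**The concern.** Toxicity from radiotherapy can show itself as a symptom that was already there and gets worse. A TEAE rule that looks only at onset cannot see this when the symptom was first recorded as an AE during screening. The device-related TEAE table is where a reader of the registration report would look for non-serious harm attributed to the device. Events dropped by this rule are, by construction, ones that deteriorated on treatment, so the omission can only make that table look better. If the rule is left open until the data are in hand, the classification becomes either a programmer's choice or a by-product of how the site kept its AE records.

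**Working it through.** No stated figure depends on this definition, so the check is a reading of the passages followed by simple arithmetic for scale.

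**1. Can an AE exist before the first treatment?** Yes. Protocol 3.1.5.2 and SAP 2.2.2 define an AE as an event during the trial, and the trial includes screening (Protocol 2.1). The Protocol summary expects about 4 weeks from consent to enrolment, and Protocol 3.1.3.1 sets enrolment at the day of first treatment. SAP 5.5.4 also tabulates all AEs separately from TEAEs. Since the TEAE window closes only at the end of the trial, AEs before treatment are the only ones that can make the two differ.

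**2. What decides membership?** The definition gives a window. The only operational rule on AE timing is SAP 4.2, which compares the start date with treatment start. The items named for the AE listing in SAP 5.5.4 include start and end dates but no date of grade change. Nothing in either document covers worsening or says that a grade rise opens a new record.

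**3. A worked record.** Suppose a grade 1 headache with a complete start date 5 days before the first treatment becomes grade 3 in week 3. It is kept as one record, judged device-related, and does not meet the SAE definition.

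| Output | Limited to TEAEs? | Event included on the onset reading? |
|---|---|---|
| All-AE tables (SAP 5.5.4) | No | Yes |
| TEAE tables | Yes | No |
| Device-related TEAE tables | Yes | No |
| SAE and device-related SAE tables | No | Only if serious |
| CTCAE grade counts (SAP 5.5.1) | No | Yes |
| AE listing | No | Yes |
| Grade 3 and grade 4/5 proportions (SAP 2.2.1) | No | Yes |

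The SAP has no category for device-related AEs outside the TEAE and SAE sets. Protocol 4.7.1 promises a summary of adverse reactions. For non-serious events, the device-related TEAE table is the only SAP table that could supply it.

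**4. Comparison with the SAP's own conservatism.** Take the same headache, still ongoing after treatment start, with its start date wholly missing. Under SAP 4.2, where "the end date is after the treatment start date or is missing, the treatment start date is used to fill in", it is dated to the first treatment and becomes a TEAE. SAP 4.4 sets a missing severity to grade 3 and counts a missing causality rating towards the device. The poorly documented event is counted, and the fully documented worsening is not.

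**5. Scale.** N = 47 (Protocol 4.2.1, SAP 1.4), assuming all enrolled subjects enter the safety set.
- One subject in one SOC, PT or severity row: at most 1/47 = 2.1 points. With 42 subjects it would be 1/42 = 2.4 points.
- The documents give no rate for such events. Assuming 1 to 4 affected subjects, a single row falls by at most 1/47 = 2.1 to 4/47 = 8.5 points, and the upper figure needs all four in that row.
- Overall TEAE incidence falls only for subjects with no other TEAE, so the effect there runs from 0 to the same ceilings.

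**The case against.** The SAP says *occurring*, not *starting*, and in the example the grade 3 headache does occur inside the window. SAP 4.2 fills in missing dates and does not define TEAE membership. If the site records the worsening as a new AE, it is counted. This stands as an ambiguity, but neither reading is written down, and onset is the only timing rule the SAP supplies.

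The affected group is also narrow. A symptom that pre-dates consent belongs to medical history (SAP 5.3.6), and its aggravation on treatment would naturally be a new event inside the window. The gap concerns symptoms that first arise in screening, worsen later and stay on one record. That limit stands in full. The protocol text available ends at section 4.10, so a recording rule in a later section or in CRF instructions cannot be excluded.

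A reader might infer that the event disappears from the report. It does not, as the table above shows.

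A reader might also infer that the safety criterion is at risk, because 2/47 = 4.3% and 3/47 = 6.4% lie on either side of 5%. The documents do not support this. Protocol 3.1.5.1 and SAP 2.2.1 define the grade 3 and grade 4/5 proportions over the whole trial cycle, Protocol 4.5 applies the failure rule to those proportions, and no TEAE-based figure is compared with 5%.

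**Conclusion.** The point holds as a gap in two sets of descriptive safety tables. On the onset-based reading, a screening-onset AE that worsens under proton therapy is left out of the TEAE and device-related TEAE tables. If it is non-serious and judged device-related, it then has no device-related table at all. The direction is favourable to the device. The size is up to 2.1 points per affected subject in any one row, and possibly nothing in overall TEAE incidence. This rests on three assumptions: that classification follows the start date, that the site does not open a new record at worsening, and that at least one such event occurs. No primary safety criterion and no report of serious events depends on it. It is still worth correcting before database lock, because the change is small and a later choice would be made with the data in view.

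**What to change.** In SAP 5.5.4, define a TEAE as an AE that starts on or after the first proton treatment, or that was present before it and increases in CTCAE grade on or after it, up to the end of the trial. Count such an event at the highest grade reached after the first treatment. Apply the same definition to device-related TEAEs. State how a grade increase is captured, either by a grade-change date or by a new AE record at the time of worsening.

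The cost is one clause in the SAP, a recording convention for the site, and some extra data handling for AEs that began in screening. Reported TEAE rates may be slightly higher. The sample size and the pass/fail rules do not change.

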5.5.5 Device defects

Calculate the number of device defects, the number of cases and the incidence rate, and describe the specific situation of the device defects in detail, including but not limited to the description of the device defect, the date of occurrence, the treatment results, etc.

5.6 Sensitivity analysis

If the receiver effectiveness index was filled by the worst observational data carry-over (WOCF) method, the sensitivity analysis of the main effectiveness measure was performed based on FAS. When the conclusions of FAS and PPS are consistent, the confidence of the test results can be enhanced. When the conclusions of the two groups are inconsistent, the analysis based on the inclusion of PPS population should be the main one, and the differences should be fully discussed and explained.

